8.2. Efficacy Analysis

Analysis of efficacy data will be carried out in the Full Analysis Set in which subjects who prematurely terminate the study will be considered failures.

The primary efficacy endpoint of the study, the ACR20 response rate, will be compared in subjects who received a given dose of ABX464 or placebo by likelihood ratio chi-square test on a 10% two-sided level.

The result of the test will be interpreted in a descriptive manner therefore no adjustment for multiple comparison is applied.

In addition, descriptive statistics will be presented by treatment arm for all secondary efficacy variables for each measurement timepoints separately for the two study groups.

These statistics include:

- Continuous variables: mean, standard deviation, minimum and maximum, stratified 95% confidence intervals, median and quartiles will be presented.
- Categorical variables: counts, rates and stratified 95% confidence intervals for the rates will be calculated.

In addition to descriptive statistics, mixed model analysis of covariance will be conducted for the following measurements:

- The change from baseline in DAS28-CRP and DAS28-ESR
- The change from baseline in the individual components of the ACR20 response (CRP, TJC(28), SJC(28), Pain-VAS, PtGA, PrGA, HAQ-DI) and in ESR
- The change from baseline in SDAI and CDAI scores
- The change from baseline in miR-124 in total blood at Week 8

In this model, treatments and stratum will be fixed effects, subjects will be random effect, and baseline values of the respective measurements will be covariates. Other explanatory variables will also be allowed to be included in the model. In order to normalize eventual skewed distributions transformation of the data will also be considered. Study groups will be compared within this model framework. All p-values will be interpreted in a descriptive manner.

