2.2 SECONDARY OBJECTIVES

The secondary objectives are the followings:

- To evaluate the effects of the different dose groups of ABX464 at Week 2, Week 4, Week 8 and Week 12 on the American College of Rheumatology (ACR) 20/50/70 response and each of its components versus placebo;
- To evaluate the effects of the different dose groups of ABX464 at Week 2, Week 4, Week 8 and Week 12 on disease activity scores (DAS28 scores, simplified disease activity score [SDAI] and clinical disease activity score [CDAI]) versus placebo;
- To evaluate the effects of the different dose groups of ABX464 at Week 2, Week 4, Week 8 and Week 12 on clinical response (DAS28 EULAR good and moderate responses), Low Disease Activity (LDA) or remission (DAS28-ESR remission, ACR/EULAR remission, SDAI and CDAI remission) versus placebo;
- To evaluate the effects of the different dose groups of ABX464 at Week 2, Week 4, Week 8 and Week 12 on the Patient Reported Outcome (PRO), Healthy Assessment Questionnaire – Disability Index (HAQ-DI);
- To evaluate the expression of miR-124 in total blood (determined by qPCR) at baseline and Week 8;
- To evaluate the effects of different dose groups of ABX464 at Week 8 on miR-124 expression in total blood versus placebo;
- To assess the pharmacokinetics of the ABX464 and its main active metabolite N-Glu-ABX464 after oral administration of different daily doses of ABX464 in patients with Rheumatoid Arthritis.

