4.2 SECONDARY EFFICACY VARIABLES

The following secondary efficacy variables will be analysed:

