4.2.2 Other secondary endpoints

- Change from Baseline in the following disease parameters at Week 2, Week 4, Week 8 and Week 12:
 - Individual components of the ACR20 response (CRP, TJC(28), SJC(28), Pain-VAS, PtGA, PrGA, HAQ-DI)
 - Erythrocyte Sedimentation Rate (ESR);
 - DAS28-CRP and DAS28-ESR. The components of DAS28 assessment include TJC(28), SJC(28), CRP/ESR, and PtGA;
 - SDAI score which includes TJC(28), SJC(28), CRP, PtGA, and PrGA;
 - CDAI score which includes TJC(28), SJC(28), PtGA, and PrGA;
 - Functional Assessment of Chronic Illness Therapy (FACIT)-Fatigue score
- Proportion of patients achieving at Week 2, Week 4, Week 8 and Week 12:
 - ACR20/50/70 response
 - Categorical DAS28-CRP response. Proportion of patients achieving categorical DAS28-CRP response will be measured as moderate/good European League Against Rheumatism (EULAR) response at each assessment time point;
 - Low Disease Activity (LDA) ($DAS28 \leq 3.2$)
 - DAS28-ESR remission ($DAS28 < 2.6$)
 - ACR/EULAR remission (TJC(28), SJC(28), CRP, and PtGA: all ≤ 1);
 - SDAI remission ($SDAI \leq 3.3$);
 - CDAI remission ($CDAI \leq 2.8$).
- Concentration of miR-124 expression in total blood (determined by qPCR) at baseline and week 8
- Change from Baseline in miR-124 expression in total blood at Week 8
- PK parameters:
 - Pre-dose plasma concentration of ABX464/N-Glu at Week 2 and Week 8;
 - Post-dose plasma concentration of ABX464/N-Glu at 1-, 2- and 3-hours post-dose at Baseline, Week 2 and Week 8;
 - Trough plasma concentration of ABX464/N-Glu at End of Study Visit
- The number of incidences of treatment-emergent serious adverse events;
- The number of incidences of treatment-emergent adverse events of special interest;
- The number of incidences of adverse events leading to investigational product discontinuation;
- The number of incidences of clinically significant laboratory abnormalities;
- The number of incidences of all AE (causally related and non-related) and SAE, further categorized by severity.

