4.4 PHARMACODYNAMIC VARIABLES

No pharmacodynamic variables will be measured.

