9.2 EXTERNAL DATA

9.2.1 Laboratory Data

Results from Local lab will be entered in CRF for Haematology, Chemistry, Pregnancy (Serum/ urine), Thyroid (for applicable sites only) and ESR (additionally for fibrinogen, troponin I & T, prothrombin time and/or INR, depending upon CSP version they get consented to).

The following table displays the clinical laboratory parameters:

HEMATOLOGY	BIOCHEMISTRY
Hemoglobin	Sodium
Hematocrit	Potassium
WBC	Chloride
Neutrophils	Calcium
Lymphocytes	Phosphate
Monocytes	Glucose
Eosinophils	BUN or urea
Basophils	Creatinine
Platelet count	AST / SGOT
ESR	ALT / SGPT
Prothrombin time and/or INR*	Alkaline phosphatase
Fibrinogen*	GLDH
	LDH
	Lipase
	Total cholesterol
	HDL cholesterol
	LDL cholesterol
	gGT
	Total bilirubin
	Total protein
	Albumin
	CRP
	T3, T4, TSH (for French sites only)
	Troponin I & T*

Tests of TB (Quantiferon TB Gold Plus), HIV (anti-HIV Ab), HCV (anti-HCV Ab), HBV (HBsAg, anti-HBs Ab), anti-HCV Ab, will be performed only at screening. * Except at Week 1 & 2

Reference ranges will be provided by the labs before site initiation and the required parameters will be transcribed onto the Data Management Laboratory Reference Range Form by the CRA. The CRA will provide reference ranges to the DM, who will use them to verify data on CRF. Further information or language translations will be provided by the responsible CRA if required.

A negative or positive result will be counted in the tables under number of positive or number of negative values. For a parameter with only a result in the comment stated that it is inferior to a certain value (< X), all data will be flagged where there is a sign "<" to count how many data are inferior to the detection limit.

No external data transfers are scheduled for this study.

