11.3.2 Secondary Variables

Descriptive statistics will be presented by treatment arm for all secondary efficacy variables for each measurement timepoints separately for the study groups:

- Proportion of patients achieving a categorical ACR20 response at Week 12 (Table 14.2.2.1 and Table 14.2.2.2).
- Change from Baseline in the individual components of the ACR20 response at Week 2, Week 4, Week 8 and Week 12 (Table 14.2.3.1 and Table 14.2.3.2):
 - C-Reactive Protein (CRP) (mg/L),
 - Tender/painful joint count (TJC) (28 joints),
 - Swollen joint count (SJC) (28 joints),
 - Patient assessment of joint pain (Pain-VAS),
 - Patient global assessment of disease (PtGA),
 - Physician's Global Assessment of Disease (PrGA),
 - HAQ-DI.
- Change from Baseline in the following disease parameters at Week 2, Week 4, Week 8 and Week 12:
 - ESR (Table 14.2.4.1.1 and Table 14.2.4.1.2);
 - DAS28-CRP (Table 14.2.4.2.1 and Table 14.2.4.2.2) and DAS28-ESR (Table 14.2.4.3.1 and Table 14.2.4.3.2);
 - SDAI score (Table 14.2.4.4.1 and Table 14.2.4.4.2);
 - CDAI score (Table 14.2.4.5.1 and Table 14.2.4.5.2);
 - FACIT-Fatigue score (Table 14.2.4.6.1 and Table 14.2.4.6.2).
- Proportion of patients achieving:
 - ACR20/50/70 response;
 - Categorical DAS28-CRP response;
 - LDA;
 - DAS28-ESR remission;
 - ACR/EULAR remission;
 - SDAI remission;
 - CDAI remission
 at Week 2, Week 4, Week 8 and Week 12 (Table 14.2.5.1 and Table 14.2.5.2).

These statistics include:

- Continuous variables: mean, standard deviation, minimum and maximum, stratified 95% confidence intervals, median and quartiles will be presented.
- Categorical variables: counts, rates and stratified 95% confidence intervals for the rates will be calculated.

In addition to descriptive statistics, mixed model analysis of covariance will be conducted for the following measurements:

- The change from baseline in DAS28-CRP and DAS28-ESR;
- The change from baseline in the individual components of the ACR20 response (CRP, TJC(28), SJC(28), Pain-VAS, PtGA, PrGA, HAQ-DI) and in ESR;
- The change from baseline in SDAI and CDAI scores.

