16 APPENDICES

16.1 STUDY FLOWCHART

	Screening Period	Study Treatment Period						Follow-up Period
	D-30 to D-1	D0	D7	D14	D28	D56	D84	D105
		W0	W1	W2	W4	W8	W12	W15
Time Window (time between two visits ≤ 30 days)			± 2 days	± 2 days	± 2 days	± 2 days	± 2 days	± 2 days
	Screening	Baseline	V1	V2	V3	V4	V5	EOS
Obtained Informed Consent	X							
Check of IN/EX Criteria	X							
Medical History	X							
Height Measurement (cm)	X							
Body Weight (kg)	X	X	X	X	X	X	X	X
Physical Examination	X	X	X	X	X	X	X	X
Vital signs	X	X	X	X	X	X	X	X
Concomitant Medications	X	X	X	X	X	X	X	X
ECG (12 lead)	X	X					X	X*
Blood Pregnancy test (WOCBP)	X				X	X	X	X
Urine Pregnancy test (WOCBP)		X						
Randomization		X						
ABX464/placebo treatment dispensation		X			X	X		
Hematology + Biochemistry#	X#	X	X	X	X	X	X	X
Blood samples drug PK (pre-dose)				X		X		X**
Blood samples drug PK (1-, 2- & 3- hours post-dose)		X		X		X		
Blood samples for Cytokines (gel tube)		X	X	X	X	X	X	
Blood samples for Cytokines (Truculture® tube)		X				X		
Blood samples for flow cytometry cells count***		X				X		
Blood samples for CRP, ESR	X	X	X	X	X	X	X	
Blood samples for miR-124 (Paxgene® tube)		X				X		
Tender Joint Count (28)	X	X		X	X	X	X	
Swollen Joint Count (28)	X	X		X	X	X	X	
Patient Global Assessment of Disease (PtGA-VAS)	X	X		X	X	X	X	
Patient assessment of Joint Pain (Pain-VAS)		X		X	X	X	X	
Investigator Global Assessment of Disease (PrGA-VAS)		X		X	X	X	X	
Health Assessment Questionnaire – Disease Index (HAQ-DI)		X		X	X	X	X	
Functional Assessment of Chronic Illness Therapy (FACIT)-Fatigue		X		X	X	X	X	
Patient diary (dispensation/check)		X	X	X	X	X	X	
Adverse Events recording	X	X	X	X	X	X	X	X
Follow up Headache Questionnaire in case of persistent headache (see section 5.3.2)			X (throughout the study, if needed)					
Dermatologist consultation in case of skin effect (see section 5.3.2)			X (throughout the study, if needed)					

#Tests of TB, HIV, HCV, HBV only at screening; *ECG at EOS visit in case of early termination only; **trough levels PK samples; ***Only in French Coordinating Investigator's Site; Two visits should not be conducted more than 30 days apart

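### SAP 11.3.2 omits the protocol's model-based Week 8 miR-124 comparison without declaring it, and the SAP assigns no output or data source to an endpoint it keeps

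*SAP*

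**What the plan says.** Protocol 8.2 names four groups of measurements for the mixed-model ANCOVA. The last is "The change from baseline in miR-124 in total blood at Week 8". The synopsis (Statistical Methods) gives the same four.

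SAP 11.3.2 introduces its own list with "mixed model analysis of covariance will be conducted for the following measurements" and gives only the first three groups, ending at SDAI and CDAI. After describing the model terms, it makes every other analysis descriptive.

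The SAP still treats miR-124 as a live endpoint:

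- SAP 2.2 keeps the objective "To evaluate the effects of different dose groups of ABX464 at Week 8 on miR-124 expression in total blood versus placebo".
- SAP 4.2 opens with "The following secondary efficacy variables will be analysed", and the list in 4.2.2 includes both the miR-124 level at baseline and Week 8 and "Change from Baseline in miR-124 expression in total blood at Week 8".
- The flowchart in SAP 16.1 schedules the miR-124 sample at Day 0 and Day 56.

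On data, Protocol 5.3.7 sends the qPCR assay to a specialised central laboratory. SAP 9.2.1 lists local-laboratory results for CRF entry, without miR-124, and adds "No external data transfers are scheduled for this study". SAP 9.2.2 expects no other non-CRF data. SAP 4.4 states "No pharmacodynamic variables will be measured", and SAP 11.5 marks pharmacodynamic (PD) analyses as not applicable. SAP 1.2, the section on changes from the protocol, mentions only the two efficacy sets.

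**The concern.** A comparison that the protocol prespecified is missing from the SAP's model list, while the objective it serves is still there. A statistician who follows the SAP would produce no dose-versus-placebo estimate for miR-124, and a reader of SAP 1.2 would not learn that anything had changed.

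miR-124 is the proposed mechanism marker, and the protocol makes it a secondary objective and endpoint. If the comparison is later run without prespecification, its model, transformation and analysis set will have been chosen after the plan was fixed. If it is not run, a stated objective goes unanswered without explanation.

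**Working it through.** There is no stated figure to reproduce. The check is a comparison of texts and a count.

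**1. Model outcomes**

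| Group | Protocol 8.2 | SAP 11.3.2 |
|---|---|---|
| DAS28-CRP, DAS28-ESR | 2 | 2 |
| ACR20 components (CRP, TJC, SJC, Pain-VAS, PtGA, PrGA, HAQ-DI) | 7 | 7 |
| ESR | 1 | 1 |
| SDAI, CDAI | 2 | 2 |
| miR-124, Week 8 | 1 | 0 |
| Total | 13 | 12 |

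**2. Outputs.** SAP 14.1 lists 6 demographic + 21 efficacy + 23 safety = 50 tables. SAP 14.2 lists 10 + 16 = 26 listings. None names miR-124. Listing 16.4.14 (Laboratory Samples Collection) has generic parameter and result columns, so it could hold a miR-124 record, but it is neither a summary nor a comparison.

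**3. Data collection.** Sampling is still planned: 60 patients × 2 visits = up to 120 sampling occasions.

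**4. Assignment.** Pharmacokinetics (PK) is the useful contrast. It is in the same 4.2.2 list and also has no transfer described in SAP 9.2, but SAP 11.4 says the CRO will not carry out that analysis. No such statement covers miR-124.

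**5. Form of a restored analysis.** There is one post-baseline miR-124 sample, so each patient contributes one change value. The variance of that value is the sum of the subject and residual components, and one record per patient cannot separate them: the information matrix for the two components has rank 1 of 2, against 2 of 2 with four visits. The random subject effect in the protocol's model is therefore redundant here. Omitting it does not alter the ANCOVA estimate.

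**6. Analysis set.** Efficacy Set 1 is defined by data at Week 12. Efficacy Set 2 carries observations forward from Week 4. Neither fits a variable measured only at baseline and Week 8, because there is no earlier post-baseline value to carry forward.

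**7. What the restored analysis could show.** With n per arm and five mean parameters (intercept, two doses, stratum, baseline), the 95% half-width for a dose-versus-placebo difference is about t(0.975, 3n − 5) × √(2/n) residual SD.

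- n = 20 (55 df): 0.63 SD.
- n = 15 with both samples (an assumption; 40 df): 0.74 SD.

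These figures describe the proposed analysis. They do not measure an error in the plan.

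**The case against.** The best defence is that SAP 11.3.2 promises descriptive statistics for all secondary efficacy variables, that SAP 4.2 files miR-124 among them, and that SAP 1.1 says the SAP is to be read with the protocol. On that view miR-124 has a stated descriptive analysis and the protocol supplies the rest. The first part stands: the endpoint has not been removed. But the itemised list after that promise omits miR-124 and gives it no table. Because everything outside the model list is descriptive, the promise does not bring back the comparison with placebo.

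It can also be said that SAP 9.2 describes only the CRO's scope, since PK concentrations have no transfer there either. This stands in part. A reader might infer from 9.2 that miR-124 data will not exist; the PK parallel shows that the inference goes too far. What the documents support is that the source and the responsible party are unassigned.

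A reader might likewise take SAP 4.4 and 11.5 as an explicit exclusion. Neither document labels miR-124 pharmacodynamic: the SAP lists it with efficacy variables, and Protocol 5.3.7 calls it an exploratory biomarker. Those sections sit awkwardly with the endpoint but do not prove it was excluded.

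Finally, the SAP's mixed model has no visit term, although its table shells have by-visit p-value rows. A reader might conclude that the model cannot fill them. Read as a separate ANCOVA at each visit, as the shells imply, it can, and only the random effect is superfluous. That wording comes from the protocol and is an editorial matter.

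**Conclusion.** The point holds as an undeclared omission. One of the protocol's 13 model-analysed outcomes, Week 8 change in miR-124, is absent from SAP 11.3.2. The objective, both endpoints and the sampling remain in the SAP, with no named table or listing and no assigned data source. Confidence is high on the list mismatch, the missing declaration and the absence of a named output.

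The consequence is for completeness and traceability. miR-124 is secondary, all p-values from these models are to be read descriptively, and the ACR20 and safety analyses do not use it. The documents set no effect size or power target for miR-124, so no loss of power can be claimed. The conclusion assumes that no separate plan outside these two documents covers the analysis. If one exists, the remaining fault is that the SAP does not say so.

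**What to change.** - **SAP 11.3.2:** add Week 8 change in miR-124 as an ANCOVA with treatment, stratum and baseline, transformed if skewed. Report each dose-versus-placebo difference with its confidence interval.
- **Analysis set:** state it as full analysis set patients with both the baseline and Week 8 samples.
- **SAP 1.2:** record that the protocol's random subject effect is omitted for this outcome because there is only one post-baseline record.
- **SAP 9.2, 14 and 15:** add the central-laboratory data transfer, one table and one listing.
- **SAP 4.4 and 11.5:** make the wording consistent with miR-124 being measured and analysed.
- **If the analysis is done elsewhere or dropped:** say so and declare it in SAP 1.2, with the reason.

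As an editorial note, the SAP could state that the other model outcomes are analysed by visit, as the shells imply.

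The cost is SAP wording, two outputs and one data transfer. The blood is already scheduled at Day 0 and Day 56, so no new samples or visits are needed.

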11.4 PK ANALYSES

PK analysis will not be conducted by Simbec-Orion.

11.5 PD ANALYSES

Not applicable.

11.6 SAFETY ANALYSES

11.6.1 Adverse Events

An overall summary table will be presented (any adverse event, any treatment emergent adverse event (TEAE), any serious adverse event (SAE), death, any grade 3 or higher adverse events from baseline to the end of Study) (*Table 14.3.1.1*). This analysis will be conducted on SAF population.

Primary safety endpoint, the rate of all treatment emergent adverse experiences, will be compared in subjects who received a given dose of ABX464 or placebo by likelihood ratio chi-square test on a 10% two-sided significance level (*14.3.1.2.1*).

Two periods will be defined for TEAE:

- Period I: any adverse event which occurs or worsens from first dosing to Day 84;
- Period II: any adverse event which occurs after Day 84.

Adverse events will be described by primary system organ class and preferred term according to the two periods. Numbers and percentage of patients, and number of occurrences of adverse event will be presented for:

- TEAE (Table 14.3.1.2.2 and Table Table 14.3.1.2.3);
- Serious TEAE (Table 14.3.1.3.1 and Table Table 14.3.1.3.2);
- TEAE leading to drug discontinuation (Table 14.3.1.4.1 and Table Table 14.3.1.4.2);
- TEAE of grade 3 or 4 (Table 14.3.1.5.1 and Table Table 14.3.1.5.2);

Further assessment of safety will be based on the frequency of adverse events (with and without regard to causality) graded according to the CTC-AE Classification and also, the review of individual values for clinical laboratory data, vital signs and ECG focusing on the detection of abnormal values and PCSAs [potentially clinically significant abnormalities (PCSAs) determined upon investigator considerations].

Adverse events will be tabulated (counts and percentages) by group. All adverse events will be listed, and the data will be tabulated by body system/organ class. Adverse event tabulations will include all treatment emergent adverse events, which will be further classified by severity, and relationship to treatment and dose level.

All adverse events (AE) will be classified using the version of the MedDRA coding dictionary specified in the DHM.

Events will be classified as treatment-emergent if they started or increased in severity on or after the first date and time of medication dosing at Visit 1 and up to study closure or withdrawal date. If an event start date is partial, then the start day, month, year or stop date will be used to determine if the event is treatment-emergent. If the classification of the AE cannot be determined from the data available, then the event will be considered treatment-emergent.

Treatment-emergent adverse events (TEAEs) will be further classified as follows:

Severe TEAEs: Severity classified as 'severe' (Common Toxicity Criteria [CTC] grade 3 or 4) or missing.

Serious TEAEs: Serious classified as 'yes' or missing.

Drug-related TEAEs: Relationship to study drug classified as 'related' or missing.

Serious drug-related TEAEs: Both serious and drug-related, as specified above.

TEAEs leading to withdrawal from study: Action taken classified as 'discontinued'.

All AE summary tables will show the number (%) of patients having at least one event and the number of events in each treatment group and overall. Median duration of AEs (from baseline to occurrence) will be presented in the tables. Note: If a patient has multiple AEs with the same preferred term, these will be summarised once within the count for N (%) of patients, but each event will be counted within the number of reports n of each AE. Changes in severity of the same AE (if collected) will be counted only once within the number of reports n of each AE.

The following will be presented in listing format within the data summaries:

- Deaths (Table 14.3.2.1);

- Serious Adverse Events (*Table 14.3.2.2*);
- Adverse Events which Led to Withdrawal (*Table 14.3.2.3*).

All adverse events (including non-treatment-emergent events) recorded on the CRF will be listed within the data listings.

